6.7.4. Mortality

For analysis of the time to death or mortality, the Kaplan-Meier method will be used. The times between surgery and the 12 months assessment will be used together with the times between surgery and the date of death. This analysis is part of the final report.

Evaluation	Level of	Recode and Analysis Plan			
Variable / Question	Measurement	Recoue and Analysis I fair			
All Assessments - Morta	lity				
Creation of variable Difference between Date of Surgery [dd.mm.yyyy] and Date of Death [dd.mm.yyyy] in [days]] (Variable(s): VISITDT; DOSEDD)	Quantitative, ratio	Case summary with number and percentage of valid cases/values, missing cases/values (if any) and total cases/values. Mean, median, interquartile range, maximum, minimum, standard deviation, 95% confidence interval for mean, Shapiro-Wilk Test.			
Creation of variable Difference between Date of Surgery [dd.mm.yyyy] and Date of 12 Months Visit [dd.mm.yyyy] in [days] J (Variable(s): VISITDT)	Quantitative, ratio	N/A (Analyzed above), used for survivorship			
Create new variable "Grouping variable - Mortality" (Variable(s): PRIMRSN)	Qualitative, nominal	 - censored = survivors - events = death 			
Create new variable "Combined Time - Mortality" (Variable(s): VISITDT; DOSEDD)	Quantitative, ratio	 Use time between surgery and 12 months visit for surviving subjects Use time between surgery and death for deceased subject 			

Use variables "Combined Time - Mortality" and "Grouping variable - Mortality" Qualitative, nominal Quantitative, ratio	Case summary with number and percentage of valid cases/values, missing cases/values (if any) and total cases/values. Kaplan-Meier survival analysis: subject ID, time, status, cumulative proportion, Kaplan-Meier estimate, standard error of KM estimate, number of cumulative events, number of remaining cases, mean for survival time with 95% confidence interval, survival graph, hazard graph.
--	---

Table 6.7.4: All Assessments – Mortality Tables List

6.7.5. Revision Surgery

For analysis of the time to the revision surgery, the Kaplan-Meier method will be used. The times between surgery and the 12 months assessment will be used together with the times between surgery and the date of revision (earliest revision in case that one subject experienced more than one revision). This analysis is part of the final report.

Evaluation Variable / Question	Level of Measurement Recode and Analysis Plan				
Adverse Events / Revision Surgery					
Creation of variable Difference between Date of Surgery [dd.mm.yyyy] and Date of First Revision [dd.mm.yyyy] in [days]] (Variable(s): VISITDT)	Quantitative, ratio	Case summary with number and percentage of valid cases/values, missing cases/values (if any) and total cases/values. Mean, median, interquartile range, maximum, minimum, standard deviation, 95% confidence interval for mean, Shapiro-Wilk Test.			
Creation of variable Difference between Date of Surgery [dd.mm.yyyy] and Date of 12 Months Visit [dd.mm.yyyy] in [days] J (Variable(s): VISITDT)	Quantitative, ratio	N/A (Analyzed above), used for survivorship			
Create new variable "Grouping variable – First Revision" (Variable(s): VISITDT)	Qualitative, nominal	 - censored = survivors - events = first (earliest) Revision 			
Create new variable "Combined Time – First Revision" (Variable(s): VISITDT)	Quantitative, ratio	 Use time between surgery and 12 months visit for surviving subjects Use time between surgery and first revision for subjects with revision(s) 			
Use variables "Combined Time – First Revision" and "Grouping variable – First Revision"	Qualitative, nominal Quantitative, ratio	Case summary with number and percentage of valid cases/values, missing cases/values (if any) and total cases/values. Kaplan-Meier survival analysis: subject ID, time, status, cumulative proportion, Kaplan-Meier estimate, standard error of KM estimate, number of cumulative events, number of remaining cases, mean for survival time with 95% confidence interval, survival graph, hazard graph.			

Table 6.7.5: All Assessments – Revision Surgery Tables List

6.7.6. SF-36 Total Physical Score – Within subject changes by visit

The within subject score changes of the SF-36 Total Physical Score from visit to visit will be analyzed to help identifying the changes on the subject level. This analysis is part of the report.

Evaluation Variable / Question	Level of Measurement	Coding and Analysis Plan			
All Assessments - SF-36 Total Physical Score Within Subject Changes					
Creation of variable "SF-36 Total Physical Score change between pre-operative visit and 3 Months [points]"	Quantitative, interval	Calculate difference (could be negative or positive).			

Difference between "SF-36 Total Physical Score Pre-Op [points]" with "SF-36 Total Physical Score 3 Months [points]" (Variable(s): VISITDT; PCSSCORE)		Case summary with number and percentage of valid cases/values, missing cases/values (if any) and total cases/values. Mean, median, interquartile range, maximum, minimum, standard deviation, 95% confidence interval for mean, Shapiro- Wilk Test.
Creation of variable "SF-36 Total Physical Score change between pre-operative visit and 6 Months [points]" Difference between "SF-36 Total Physical Score Pre-Op [points]" with "SF-36 Total Physical Score 6 Months [points]" (Variable(s): VISITDT; PCSSCORE)	Quantitative, interval	Calculate difference (could be negative or positive). Case summary with number and percentage of valid cases/values, missing cases/values (if any) and total cases/values. Mean, median, interquartile range, maximum, minimum, standard deviation, 95% confidence interval for mean, Shapiro- Wilk Test.
Creation of variable "SF-36 Total Physical Score change between pre-operative visit and 12 Months [points]" Difference between "SF-36 Total Physical Score Pre-Op [points]" with "SF-36 Total Physical Score 12 Months [points]" (Variable(s): VISITDT; PCSSCORE)	Quantitative, interval	Calculate difference (could be negative or positive). Case summary with number and percentage of valid cases/values, missing cases/values (if any) and total cases/values. Mean, median, interquartile range, maximum, minimum, standard deviation, 95% confidence interval for mean, Shapiro- Wilk Test.
Creation of variable "SF-36 Total Physical Score change between 3 Months and 6 Months [points]" Difference between "SF-36 Total Physical Score 3 Months [points]" with "SF-36 Total Physical Score 6 Months [points]" (Variable(s): VISITDT; PCSSCORE)	Quantitative, interval	Calculate difference (could be negative or positive). Case summary with number and percentage of valid cases/values, missing cases/values (if any) and total cases/values. Mean, median, interquartile range, maximum, minimum, standard deviation, 95% confidence interval for mean, Shapiro- Wilk Test.
Creation of variable "SF-36 Total Physical Score change between 3 Months and 12 Months [points]" Difference between "SF-36 Total Physical Score 3 Months [points]" with "SF-36 Total Physical Score 12 Months [points]" (Variable(s): VISITDT; PCSSCORE)	Quantitative, interval	Calculate difference (could be negative or positive). Case summary with number and percentage of valid cases/values, missing cases/values (if any) and total cases/values. Mean, median, interquartile range, maximum, minimum, standard deviation, 95% confidence interval for mean, Shapiro- Wilk Test.
Creation of variable "SF-36 Total Physical Score change between 6 Months and 12 Months [points]" Difference between "SF-36 Total Physical Score 6 Months [points]" with "SF-36 Total Physical Score 12 Months [points]" (Variable(s): VISITDT; PCSSCORE)	Quantitative, interval	Calculate difference (could be negative or positive). Case summary with number and percentage of valid cases/values, missing cases/values (if any) and total cases/values. Mean, median, interquartile range, maximum, minimum, standard deviation, 95% confidence interval for mean, Shapiro- Wilk Test.

Table 6.7.6: All Assessments – SF-36 Total Physical Score Within Subject Changes

7. Table Templates (Tables, Figures, Listings - TFL)

Tables must consist of at least a headline, the variable/analysis-object label and column headers. Furthermore, the table headline must contain the "Analysis Section"(e.g. Demographics, Operative) the variable label (e.g. Gender, Age) as well as the table type (Frequencies, Listing). If the table is referring to a subgroup, a notification must be entered in the headline as well. Figures (if any) must be clearly labeled and numbered by a figure number and title in addition to the axis and category labeling created by software packages (e.g. IBM SPSS).

7.1. FREQUENCIES

All answered response options must be listed with the appropriate label, other response options do not have to be displayed necessarily. In the event of missing answers, the frequencies must be included in an extra row as well ("*Missing*"). All given answers must be added up in an extra row ("*Total*"). In addition to the number of frequencies, percentages must be displayed in a separate column.

"Analysis Section" – "Variable Label" – Frequencies					
Characteristic		n	%		
"Variable Label"	"Response A"	"xxx"	"xxx "		
	"Response B"	"xxx "	"xxx "		
	Missing	"xxx "	"xxx "		
	Total	"xxx"	"xxx "		

"Analysis Section" – "Variable Label" – Frequencies

Table 7.1.1: Frequencies Table Template

If multiple subgroups/clusters (e.g. Sites, Visits) should be displayed in one table, an extra column ("*Group X*") and/or extra rows ("*Group Y*") must be added. Same applies to (sub-) questions, which can be merged in one table. It is recommended to add an extra "Total" column and row, for adding up the subgroups, if possible, from a statistical point of view. In addition, subgroups must be named in the headline as well ("*by Group X and by Group Y*").

"Analysis Section" – "Variable Label" – Frequencies – by "Group X" and "Group Y"

Characteristic		"Group X1"		"Group X2"		Total	
		n	%	n	%	n	%
	"Response A"	"xxx "	"xxx"	"xxx "	"xxx"	"xxx"	"xxx"
"Crown VI"	"Response B"	"xxx "	"xxx"	"xxx"	"xxx "	"xxx"	"xxx"
Group II	Missing	"xxx "	"xxx"	"xxx"	"xxx "	"xxx"	"xxx"
Total	Total	"xxx "	"xxx"	"xxx"	"xxx "	"xxx"	"xxx"
	"Response A"	"xxx "	"xxx"	"xxx"	"xxx"	"xxx"	"xxx "
"Crown V2	"Response B"	"xxx "	"xxx"	"xxx"	"xxx"	"xxx"	"xxx"
Group 12	Missing	"xxx "	"xxx"	"xxx"	"xxx"	"xxx"	"xxx"
	Total	"xxx "	"xxx"	"xxx "	"xxx"	"xxx"	"xxx"
	"Total Response A"	"xxx "	"xxx"	"xxx "	"xxx"	"xxx"	"xxx"
Total	"Total Response B"	"xxx "	"xxx"	"xxx "	"xxx"	"xxx"	"xxx"
	Missing	"xxx "	"xxx"	"xxx"	"xxx"	"xxx"	"xxx"
	Total	"xxx"	"xxx"	"xxx"	"xxx"	"xxx"	"xxx"

Table 7.1.2: Grouped Frequencies Table Template

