8.2. SECONDARY ENDPOINTS

- Safety: Incidence of device-related adverse events by 12 months will be monitored through collection and analyses.
- Efficacy/Performance: Bone consolidation will be assessed by 12 months as measured by Investigator assessment.

9. Selection of Clinical Investigation Population

Subjects participating in this clinical investigation will be recruited from the investigator's standard subject population, where all subjects presenting for treatment of tibial fractures will be evaluated for clinical investigation participation based on the eligibility criteria listed below.

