3.1.2. Secondary Analyses

For efficacy/performance, bone consolidation will be assessed by 12 months as measured by Investigator assessment. For Safety, the incidence of device-related adverse events/incidents by 12 months will be monitored through collection and analyses. Both analyses will be part of the final report.

Furthermore, device related adverse events/incidents and the time to (earliest) Device Related Adverse Events/incidents will be analyzed as well. Considered variables, the level of measurement and the planned analysis steps are listed in detail in the SAP.

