6.1. HARMS AND SAFETY

Categorization and definitions of (Serious-, Unanticipated-) Adverse Device Effects, (Serious-) Incidents are given in the CIP.

Evaluation Variable / Question	Level of Measurement	Analysis Plan	Iı	nclusio	on
Adverse Events / Incidents	incusur ement		IR	FR	N/A
Device-Related Adverse Event / Incident (Variable(s): AEEVENT; AEOTHER)	Qualitative, nominal	Proportions, frequencies, column and row totals, missing proportion (if any). Listing of other Events/Incidents.	х	х	
Describe the AE/Incident (Variable(s): AEDESCRP)	Qualitative, nominal	Listing of other Events/Incidents Description.			Х
Unanticipated Adverse Device Event? (Variable(s): AEUADE)	Qualitative, nominal	Proportions, frequencies, column and row totals, missing proportion (if any).	Х	Х	
Severity (Variable(s): AESEVER)	Qualitative, nominal	Proportions, frequencies, column and row totals, missing proportion (if any).	Х	Х	
Describe Treatment: (Variable(s): ACTTREAT)	Qualitative, nominal	Listing of Treatment Description.			X
Action Taken (Variable(s): ACTNONE; ACTMEDS; ACTSURG; ACTLABOT; ACTSHORT; ACTPROHS; ACTOTHER: ACTOTHSP)	Qualitative, nominal	Proportions, frequencies, column and row totals, missing proportion (if any). Listing of given Other specifications.			X
AE Resolution (Variable(s): AERESOLV)	Qualitative, nominal	Proportions, frequencies, column and row totals, missing proportion (if any).			Х
Outcome (Variable(s): AEONWOTR; AEONWTTR; AEREWOTR; AEREWTTR; AETEDISB; AEPERMD; AESUEXP)	Qualitative, nominal	Proportions, frequencies, column and row totals, missing proportion (if any).			х
Creation of variable Number of Adverse Device Effects by Site (Variable(s): AEEVENT; SITENUM)	Qualitative, nominal	Proportions, frequencies, column and row totals, missing proportion (if any).	Х	Х	
Creation of variable Number of Adverse Device Effects per Subject and Site (Variable(s): AEEVENT; SITENUM; SUBID)	Qualitative, nominal	Proportions, frequencies, column and row totals, missing proportion (if any).	Х	Х	
Creation of variable Number of Adverse Device Effects by Visit (Variable(s): AEEVENT: VISNAME)	Qualitative, nominal	Proportions, frequencies, column and row totals, missing proportion (if any).		Х	

Table 6.1: Adverse Events / Incidents Tables List

Evaluation Variable / Question	Level of Measurement	Analysis Plan Inclusion		on	
Reoperation			IR	FR	N/A

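### SAP Table 6.1 and template 7.1 name no subject denominator, so no planned table reports incidence of device-related events by type, severity or UADE

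*SAP*

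**What the plan says.** Protocol 8.2 defines the secondary safety endpoint: "Incidence of device-related adverse events by 12 months will be monitored through collection and analyses". SAP 3.1.2 repeats it: "the incidence of device-related adverse events/incidents by 12 months will be monitored through collection and analyses".

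SAP Table 6.1 tabulates the event type (AEEVENT, AEOTHER), the UADE flag (AEUADE) and severity (AESEVER) as frequencies and proportions with totals, for annual and final reports. It adds counts by site, and a row headed "Number of Adverse Device Effects per Subject and Site" that uses SUBID. Both of these are also marked for annual and final reports.

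The template in SAP 7.1 sets the Total row: "All given answers must be added up in an extra row". It then requires percentages: "In addition to the number of frequencies, percentages must be displayed in a separate column". Response options that nobody chose may be left out. Neither 6.1 nor 7.1 says what the percentage is a percentage of.

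Three other places bear on the point:

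- SAP Table 6.6.3, labelled a secondary endpoint table, takes each subject's first device-related event of any type and plans a Kaplan-Meier analysis, for the final report only.
- SAP Table 5.1 gives subject counts by site in annual and final reports.
- SAP 4.6 relates missing cases to enrolled cases, but says nothing about the base for event percentages.

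**The concern.** An incidence needs the subjects at risk as its denominator. The variables in Table 6.1 describe individual events, and Protocol 13.2 captures only events judged possibly, probably or definitely device-related. A subject without such an event would therefore be expected to have no AEEVENT answer. If the Total is the sum of given answers and the percentage is taken on that Total, each percentage is a share of event reports. Those shares sum to 100% whatever the risk, a subject with several reports counts several times, and the result does not change with the number of subjects who received the nail.

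A reader who takes such a figure as the risk of pain, or of a severe or unanticipated event, would be misled. These breakdowns are the main detail on the safety of the nail in a single-arm post-market study.

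**Working it through.** The documents state no adverse event rate or count, so there is no planned figure to reproduce. The check has two parts.

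**Which planned table yields which incidence**

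| Quantity | Annual reports | Final report |
|---|---|---|
| Any device-related event, per subject | Not printed; approximated from the per-subject row and the Table 5.1 site counts | One minus the Kaplan-Meier estimate, Table 6.6.3 |
| By event type, severity or UADE, per subject | Not given | Not given |

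The per-subject row counts events for each subject, so subjects with at least one event can be identified. It does not split them by type, severity or UADE, and it defines neither a zero-event category nor a denominator. Table 6.6.3 pools all event types.

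**What the percentages would show**

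Inputs: 80 treated subjects, taken from the planned enrolment in SAP 2.2. All event counts are assumptions for illustration.

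Formulas:

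- Template percentage = reports of one type / all reports
- Any-event incidence = subjects with at least one event / subjects treated, with an exact 95% interval

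| Assumed subjects with an event | Reports | Pain reports | Subjects with pain | Template pain % | Pain incidence | Any-event incidence (95% CI) |
|---|---|---|---|---|---|---|
| 4 | 6 | 3 | 3 | 3/6 = 50.0% | 3/80 = 3.75% | 4/80 = 5.0% (1.4 to 12.3) |
| 8 | 12 | 5 | 4 | 5/12 = 41.7% | 4/80 = 5.0% | 8/80 = 10.0% (4.4 to 18.8) |
| 16 | 24 | 10 | 8 | 10/24 = 41.7% | 8/80 = 10.0% | 16/80 = 20.0% (11.9 to 30.4) |

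Between the second and third rows both incidences double while the template percentage does not move. The same happens when the denominator changes: the 8-subject record gives 41.7% whether 80 subjects were treated (8/80 = 10%) or 40 (8/40 = 20%).

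The frequency column allows only a bound. Five pain reports could come from one to five subjects, so pain incidence lies between 1/80 = 1.25% and 5/80 = 6.25%.

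**A limit of the Kaplan-Meier table**

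Table 6.6.3 gives event-free subjects the time to their 12-month visit and states no time for those without that visit. If they drop out of the analysis, then with 8 event subjects and 10% to 20% of the 72 event-free subjects lost (7 to 14), the figure becomes 8/73 = 11.0% to 8/66 = 12.1%, against 8/80 = 10.0% crude.

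**The case against.** The strongest reply is that SAP 6.6, not 6.1, is the endpoint section. Table 6.6.3 counts each subject once and allows a 12-month any-event incidence to be read off. A reader might infer that the safety endpoint has no subject-level analysis at all; the documents do not support that. What the table lacks is any breakdown by type, severity or UADE, and any place in the annual reports. Protocol 11.3.3 puts the safety analysis in annual and final reports, while SAP 3.1.2 says final report only. That conflict needs its own resolution, and this point does not rest on it.

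A reader might also infer that the SAP instructs the programmer to divide by event reports. It does not: the base is undefined, and shares of reports are only the natural reading. That event-free subjects have no answer is likewise inferred, since the form and export are not shown, and a created per-subject count could take the value zero.

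A third tempting reading is that the by-site row would suggest site differences that do not exist. With equal risk and assumed enrolment of 40, 20, 10, 5 and 5, site shares of all events would be 50, 25, 12.5, 6.25 and 6.25%, an apparent eightfold contrast. That follows only if percentages run across sites, and neither Table 6.1 nor 7.1 fixes the direction. The per-subject row and Table 5.1 also let a reader approximate any-event incidence by site.

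Finally, no safety hypothesis or stopping rule depends on these percentages, and the counts stand beside them. This limits the consequence but does not supply the missing incidence.

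**Conclusion.** The point holds as a gap in specification. Table 6.1 and template 7.1 name no subject denominator, and no row prints subjects with at least one device-related event over subjects treated. Any-event incidence is available in the final report from Table 6.6.3, and by approximation in the annual reports. Incidence by type, severity or UADE is not given in either.

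Its size cannot be stated from the documents because no event rate is given. The illustration shows the kind of error: 41.7% printed for pain where the incidence is 5% or 10%. It rests on assumed counts, one record per event, and the natural reading of the percentage base. The primary endpoint is unaffected. The plan should be changed because a named endpoint should not leave its denominator to the programmer and the data needed are already collected.

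**What to change.** In SAP Table 6.1, for the reports in which it already appears:

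- Add the number and percentage of subjects with at least one device-related event, overall and by event type, worst severity, UADE and site. Count each subject once per row.
- Use as denominator all subjects in whom the nail was implanted, overall or at that site, including those with no event. Define this set in SAP 5.1, which has only ITT and PP. ITT can include subjects who did not receive the nail, and PP can leave out implanted subjects with a protocol violation.
- Show event counts in a separate column without a percentage.
- Show follow-up status beside the crude percentages in both annual and final reports.

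In SAP 7.1, state that the rule totalling given answers does not set the percentage base for event forms.

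Keep the Table 6.6.3 Kaplan-Meier estimate as the 12-month any-event incidence that allows for incomplete follow-up. For it to do so, state the censoring time for event-free subjects without a 12-month visit.

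The cost is SAP wording and one programming step, a merge of the event form with the list of implanted subjects by SUBID. No new data are needed. The small downside is that crude percentages include subjects not followed to 12 months, which is why follow-up status must stand beside them.

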7.2. DESCRIPTIVE STATISTICS

Descriptive Statistic tables must contain the items listed in Table 7.2.1. Furthermore, the associated unit must be displayed. If the values are referring to a subgroup (n) and not to the overall population (N), a notification must be entered in the headline("n = xxx").

Statistics $(n = "xxx")$				
Characteristic		[" unit "]		
"Variable Label"	Mean	"xxx"		
	Median	"xxx"		
	SD	"xxx"		
	IQR	"xxx"		
	Max	"xxx"		
	3.61			

"Analysis Section" – "Variable Label" – Descriptive	
Statistics $(n = "xxx")$	

 Min
 "xxx"

 Table 7.2.1: Descriptive Statistics Table Template

